## 1. OBJECTIVES

### 1.1. Primary objective

- 1.1.1. Determine sensitivity, specificity, positive, and negative predictive value of  $^{68}\text{Ga}$  PSMA-HBED-CC PET for detection of regional pelvic nodal metastases compared to pathology at radical prostatectomy (per patient, using nodal regional correlation).

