## 5.6. **Post-Imaging Prostatectomy**

Prostatectomy and pelvic nodal dissection will be performed at the discretion of referring physician after reviewing imaging results. Nodal dissection should follow standard of care.

- 5.6.1. **Negative imaging.** Subjects without evidence of positive nodal or metastatic disease on  $^{68}\text{Ga}$  PSMA-HBED-CC PET imaging will undergo radical prostatectomy and pelvic nodal dissection. The pelvic nodal dissection will be performed regardless of imaging results.
- 5.6.2. **Positive imaging.** The urologist will be informed of the location of any  $^{68}\text{Ga}$  PSMA-HBED-CC PET positive (or suspicious) regional pelvic nodes prior to surgery. The surgeon should attempt to capture the suspicious node during the nodal dissection.
- 5.6.3. **Nodal dissection.** Nodes will be marked by location using the standard procedures. For example, if the urologist removed left and right nodal regions separately, the subject will have two nodal regions (left/right). If the nodes are removed in six groups (bilateral internal/external/obturator nodes), the subject will have six nodal regions analyzed.
- 5.6.4. **Pathology:** Specimens from prostatectomy will be evaluated for the presence of nodal metastasis. This will be reported on a per patient basis, and by region as positive or negative. The pathology report should list the number of nodes counted during the exam.
- 5.6.5. **Immunohistochemical staining (IHC) (optional).** Although not routinely performed during standard practice, IHC staining for PSMA of tumor specimens (primary and lymph node metastases) is preferred.

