12.2.1.3. Bone lesions: Given the high rate of false negative biopsies for osseous metastases in subjects with prostate cancer, subjects with negative bone biopsies of  $^{68}\text{Ga}$ -PSMA-HBED-CC PET positive lesions will be further evaluated:

- If pathology demonstrates an alternative diagnoses that is known to be  $^{68}\text{Ga}$ -PSMA-HBED-CC positive (eg Renal Cell Carcinoma metastases, Paget's disease), then this will be considered negative for disease.
- If pathology is indeterminate, then follow-up imaging as described below will be performed as per clinical standards at the site.

12.2.1.4. Although not routinely performed during standard practice, immunohistochemical staining for PSMA of tumor specimens (primary and lymph node metastases) may be performed, although not required.

12.2.1.5. All regions not sampled for biopsy/histopathology will be designated as indeterminate for disease by pathology. Conventional imaging follow-up may be used in these cases to determine tissue status.

12.2.2. Follow-up Imaging will be used as a secondary assessment for prostate cancer in the event pathology information is not available:

All subjects will be tracked for follow-up conventional imaging between 3-12 months post  $^{68}\text{Ga}$ -PSMA-HBED-CC (dedicated CT, MRI and/or bone scan) as per site standard of care. If no follow-up imaging has been performed within the 9 months following the  $^{68}\text{Ga}$ -PSMA-HBED-CC scan, then the research study will pay for an additional follow-up CT scan to be performed in the 9-12

month window post-Ga-PSMA-HBED-CC scan. Follow up imaging will only be performed on subjects that have positive Ga-PSMA-HBED-CC findings because conventional imaging assessment for disease is primarily targeting suspicious lesions identified by Ga-PSMA-HBED-CC PET/CT. Interpretation of follow-up imaging will be performed by local read. Preferably, the follow-up conventional imaging should be the same modality/modalities as the initial staging work-up to allow for reproducible and accurate comparisons. Conventional imaging standards as described below will be used to determine tissue positive for prostate cancer disease. Conventional imaging will not be used to determine negative prostate cancer disease regions due to its inherently low negative predictive value.

Tissue positive for prostate cancer disease based on follow-up imaging:

12.2.2.1. Lymph nodes will be assessed by change in size.

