## 13. STATISTICAL CONSIDERATIONS

### 13.1. Statistical Justification

This study is a pilot study to determine target sensitivity for Ga PSMA-HBED-CC for the detection of prostate cancer in the pre-prostatectomy population. Based upon literature, we anticipate sensitivities of > 80% in this patient population, but there are uncertainties, particularly related to the proposed reference standard. We plan to use the results of this pilot study, potentially combined with reported results from other sites across the US performing similar studies (same patient population, same methods, same reference standard definitions...) to determine most-appropriate primary endpoint sensitivities for a larger University of Iowa study to follow this one, so as to appropriately statistically power the larger study.

The primary objective of this pilot study is to obtain preliminary information on the sensitivity of physician reads for Ga-68 PSMA pre-prostatectomy; physicians' ability to correctly identify prostate cancer and metastases via Ga-68 PSMA relative to our pathology/conventional imaging reference standard. Due to the lack of clinical experience with this radiopharmaceutical, this pilot study is meant to gain meaningful information of the sensitivity of this agent in this patient population to generate hypotheses for further trials.

To evaluate sensitivity, patients must undergo both Ga-68 PSMA imaging and evaluation for prostate cancer by pathology, follow-up conventional imaging, or both. Sensitivity is defined as:

$$Sensitivity = \frac{\text{number of true positives (TP)}}{\text{number of true positives (TP)} + \text{number of false positives (FP)}}$$

The table below provides 95% confidence interval half-widths for a range of sensitivity values based on a planned sample size of 30 patients using a normal approximation.

Sensitivity	Half-Width
70%	16.4%
75%	15.5%
80%	14.3%
85%	12.8%
90%	10.7%

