#### 13.2.1. True positive patient:

13.2.1.1. **Ga PSMA-HBED-CC PET/CT positive for a regional node by internal blind reader:** pathology at prostatectomy is positive for a regional node that correlates in location to the PET images (location on pathology is determined by the urologist at the time of the surgery). Only one node needs to correspond between imaging and pathology for a patient to be considered a true positive.

13.2.1.2. **Ga PSMA-HBED-CC PET/CT positive for regional nodes by internal blind reader,** pathology negative for regional nodes, imaging after prostatectomy demonstrates the same node was not removed at surgery, and follow-up biopsy or imaging demonstrates presence of nodal disease as defined in Section 12.2.1.2 .

13.2.1.3. **Conventional imaging criteria for positive node on follow-up imaging:** imaging within 3-12 months, the node decreases by more than 30% (for patients undergoing systemic treatment or focal therapy at this site) or increase by more than 20% in short axis diameter in the absence of treatment (with a minimum of 3 mm in change in size) as defined in Section 12.2.2.1 .

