#### 13.2.2. True negative patient:

13.2.2.1. **Ga PSMA-HBED-CC PET/CT negative for regional nodes by internal blind reader;** pathology at prostatectomy negative for regional nodes as defined in Section 12.2.1.2 .

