#### 13.2.3. False positive patient:

13.2.3.1. **Ga PSMA-HBED-CC PET/CT positive for regional nodes**

**by internal blind reader**, pathology at prostatectomy is negative, and imaging after prostatectomy demonstrates that node is no longer present as defined in Section 12.2.1.2.

13.2.3.2.  **$^{68}\text{Ga}$  PSMA-HBED-CC PET/CT positive for regional node by internal blind reader**, but pathology at prostatectomy is positive for node but in a different nodal region than the node seen on PSMA PET.

13.2.4. False negative patient:

13.2.4.1.  **$^{68}\text{Ga}$  PSMA-HBED-CC PET/CT negative for regional nodes by internal blind reader**, but pathology at prostatectomy is positive for regional nodes.

13.2.5. Non-evaluable patient:

13.2.5.1. Any subject that does not have sufficient data to meet the criteria for definition of true positive patient, true negative patient, false positive patient, or false negative will be classified as non-evaluable.

13.2.5.2. Patients with extrapelvic nodal metastases will not be included in this analysis for the primary endpoint if patients do not undergo prostatectomy.

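### The primary endpoint is scored against a composite reference that can reclassify only PET-positive, pathology-negative men, whereas objective 1.1.1 promises a comparison with prostatectomy pathology; both tables should be reported

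*Combined protocol and SAP*

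**What the plan says.** The comparator is stated in two ways. Objective 1.1.1 sets PET "compared to pathology at radical prostatectomy (per patient, using nodal regional correlation"). Section 13.1 describes performance "relative to our pathology/conventional imaging reference standard", and section 12.2 defines that composite in detail.

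The patient-level rules in 13.2 are:

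- **True positive.** Besides a pathology match, 13.2.1.2 admits a PET-positive, pathology-negative man when "imaging after prostatectomy demonstrates the same node was not removed at surgery, and follow-up biopsy or imaging demonstrates presence of nodal disease". Section 13.2.1.3 adds size-change criteria. It names no PET result but is listed only under true positive.
- **False positive.** 13.2.3.1 applies when "pathology at prostatectomy is negative, and imaging after prostatectomy demonstrates that node is no longer present". 13.2.3.2 adds men whose positive pathology lies in a different nodal region.
- **True negative.** PET negative and "pathology at prostatectomy negative for regional nodes as defined in Section 12.2.1.2".
- **False negative.** PET negative, "but pathology at prostatectomy is positive for regional nodes".
- **Non-evaluable.** 13.2.5.1 takes anyone who fits none of these.

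Extra investigation depends on the PET result. For PET-positive nodes, "The surgeon should attempt to capture the suspicious node during the nodal dissection" (5.6.2). The optional rescan (5.7.1) and second PSMA PET (6.4.4) are for men with a positive PET and negative pathology. On study follow-up imaging, 12.2.2 says: "Follow up imaging will only be performed on subjects that have positive" PET findings.

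**The concern.** The reference standard is strengthened only where PET was positive. A node missed by the dissection is possible in either group, but only the PET-positive man can have his pathology result overturned. Of the two discordant groups, one can be moved in PET's favour; among the concordant negatives, nobody can be moved against it.

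The secondary rules are more even-handed. Under 13.3.2 a true-negative region must also not be positive on imaging, and 13.3.4 allows a false negative through follow-up imaging. The primary endpoint has neither provision.

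There is also a quiet exit. The rescan is optional and 13.2.3.1 needs imaging proof that the node is gone, so a potential false positive who is not rescanned can leave the table as non-evaluable.

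At stake is the pilot's main output. Section 13.1 says the results will help choose the sensitivity used to power a larger study, and itself names the reference standard as a source of uncertainty. Without a pathology-only table nobody can see how much of the estimate comes from reclassification.

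**Working it through.** **The plan's own figures.** The half-widths in 13.1 are 1.96 × √[p(1−p)/30]. For p = 70, 75, 80, 85 and 90% this gives 16.4, 15.5, 14.3, 12.8 and 10.7 points, as printed. They do not depend on the scoring rule. Section 13.1 prints the sensitivity formula with false positives in the denominator, which is PPV; below, sensitivity is TP/(TP+FN).

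**Direction, against pathology only.**

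- *FP to TP.* Sensitivity becomes (TP+1)/(TP+1+FN), a gain of FN/[(TP+FN)(TP+FN+1)], which is never negative. Specificity becomes TN/(TN+FP−1) and PPV becomes (TP+1)/(TP+FP). NPV = TN/(TN+FN) contains neither moved cell, so it does not change.
- *FP to non-evaluable.* Specificity and PPV lose one from the denominator. Sensitivity and NPV do not change.
- *Check.* Over all 4,960 tables of 30 men with at least one FP, neither move lowered any of the four measures.

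**Size, from the documents.** Section 2.3 reports a prospective 30-man study with sensitivity 64%, specificity 95%, PPV 88% and NPV 82%. Only one table of 30 reproduces these: TP 7, FN 4, FP 1, TN 18 (7/11, 18/19, 7/8, 18/22). The last three rows assume that equal follow-up finds nodal disease in 1, 2 or 3 of the 18 true negatives; the documents give no rate.

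| Scoring | TP/FN/FP/TN | Sens | Spec | PPV | NPV |
|---|---|---|---|---|---|
| Pathology only (1.1.1) | 7/4/1/18 | 63.6% | 94.7% | 87.5% | 81.8% |
| FP moved to TP (13.2.1.2) | 8/4/0/18 | 66.7% | 100% | 100% | 81.8% |
| FP made non-evaluable | 7/4/0/18 | 63.6% | 100% | 100% | 81.8% |
| FP to TP, and 1 TN to FN | 8/5/0/17 | 61.5% | 100% | 100% | 77.3% |
| FP to TP, and 2 TN to FN | 8/6/0/16 | 57.1% | 100% | 100% | 72.7% |
| FP to TP, and 3 TN to FN | 8/7/0/15 | 53.3% | 100% | 100% | 68.2% |

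Against pathology, the sensitivity gain is 4/(11 × 12) = 3.0 points. Against equal follow-up, the one-way rule overstates sensitivity by 66.7 − 61.5 = 5.1 points (unrounded) up to 66.7 − 53.3 = 13.3 points, and NPV by 4.5 to 13.6 points, over the assumed range.

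**Which table is nearer to equal follow-up?** Take an assumed table with more false positives, 6/4/3/17. Two FPs are truly retained disease, and equal follow-up would also find disease in two TNs.

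| Scoring | TP/FN/FP/TN | Sens | Spec | PPV | NPV |
|---|---|---|---|---|---|
| Equal follow-up | 8/6/1/15 | 57.1% | 93.8% | 88.9% | 71.4% |
| Plan's composite | 8/4/1/17 | 66.7% | 94.4% | 88.9% | 81.0% |
| Pathology only | 6/4/3/17 | 60.0% | 85.0% | 66.7% | 81.0% |

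The composite matches on PPV and is within one point on specificity. Pathology only is closer on sensitivity, but 8.8 points low on specificity and 22.2 points low on PPV. Both miss NPV by the same amount.

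**The case against.** The strongest reply is that 13.2.1.2 repairs a real failure of the reference. Pathology never examined a node left in the patient, and the rule demands both proof that it was left and later evidence of disease. This stands, and the last table shows that a pathology-only analysis can be the worse guide to specificity and PPV. It also leaves disease missed in PET-negative men uncorrected. A reader might infer that the pathology-only table should replace the composite as primary; the documents do not support that.

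Four other strong readings also go too far.

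- *That the rule can only raise every accuracy figure.* NPV does not change against pathology, and dropping a man as non-evaluable leaves sensitivity alone. A retained node biopsied negative counts as disease-free under 12.2.1.2, so not every retained node favours PET. Rule 13.2.3.2 works against PET on specificity and PPV.
- *That the composite is a concealed change.* It is set out in 12.2 and named in 13.1. The fault is an unreconciled objective.
- *That PET-negative men get no further look.* Pathology, standard-of-care imaging and PSA to 12 months are collected without restriction to PET-positive men (6.4.1 to 6.4.3). The gap is that the primary scoring rules do not use them.
- *That the larger trial will be mis-sized.* The documents do not say which reference it will use, so this is a risk only.

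It is also fair that the analysis is descriptive, and that a 3-point shift is small beside the sampling error: with 11 node-positive men the half-width at 63.6% is 1.96 × √(0.636 × 0.364/11), about 28 points. That limits the severity. It does not remove a shift whose direction is known in advance.

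**Conclusion.** The concern holds in limited form. The reference in 13.2 differs from the one in 1.1.1, and reclassification depends on a positive PET. Relative to pathology, sensitivity, specificity and PPV can be raised or left unchanged but never lowered, and NPV is unaffected. Relative to equal follow-up, the distortion falls mainly on sensitivity and NPV.

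The actual size cannot be derived from the documents. The one document-based example rests on a single false positive. The equal-follow-up rows and the three-false-positive table rest on assumed counts; that table implies 85% specificity, against 95% and 98.9% in the two cited pre-prostatectomy studies. The issue is moderate: it does not invalidate the pilot, but it leaves an avoidable and invisible component in the sensitivity it is meant to deliver.

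**What to change.** 1. Report a pathology-only 2x2 table that answers 1.1.1, with every operated PET-positive, pathology-negative man counted as a false positive, side by side with the composite table, labelled as such. Reconcile the wording of 1.1.1 with 13.1. Keep the location rule 13.2.3.2 in both tables.
2. Print how many men moved from false positive to true positive and how many to non-evaluable. Show the composite with unresolved PET-positive, pathology-negative men counted first as all true positive, then as all false positive.
3. In the composite, let the pathology and standard-of-care imaging already collected to 12 months (6.4.1, 6.4.2) turn a PET-negative, pathology-negative man into a false negative, as 13.3.4 does for secondary regions. State how this fits with the 60-day pathology window in 12.2.1, and that such follow-up is less complete in PET-negative men.

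The cost is some wording, a little extra analysis and slightly less favourable figures. No new data and no change to patient care are needed. In the pathology-only table a node left in place counts against PET, and in the composite follow-up remains unequal. Neither table is unbiased, which is why both should be shown.

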13.3.2. True negative region

13.3.2.1.  **$^{68}\text{Ga}$  PSMA-HBED-CC PET negative for extra-pelvic node metastases by internal blind reader** – and pathology (if available) negative for disease, and, extra-pelvic node not positive for disease by imaging.

13.3.2.2.  **$^{68}\text{Ga}$  PSMA-HBED-CC PET negative for visceral metastases by internal blind reader** – and pathology (if available) negative for disease, and, visceral lesion not positive for disease by imaging.

13.3.2.3.  **$^{68}\text{Ga}$  PSMA-HBED-CC PET negative for osseous metastases by internal blind reader** - and pathology (if available) negative for disease, and, osseous lesion not positive for disease by imaging.

13.3.3. False positive region:

13.3.3.1.  **$^{68}\text{Ga}$  PSMA-HBED-CC PET positive for extra-pelvic nodes by internal blind reader**, pathology (if available) is negative, and imaging after prostatectomy demonstrates that node is not positive for disease.

13.3.3.1.1.  **$^{68}\text{Ga}$  PSMA-HBED-CC PET positive for regional node by internal blind reader**, but pathology (if available) is positive for node but in a different nodal region than the node seen on PSMA PET.

13.3.3.2. **PSMA-HBED-CC PET positive for visceral lesion by internal blind reader**, pathology (if available) is negative, and imaging after prostatectomy demonstrates that the visceral lesion is not positive for disease.

13.3.3.2.1.  **$^{68}\text{Ga}$  PSMA-HBED-CC PET positive for visceral lesion by internal blind reader**, but pathology (if available) is positive for visceral lesion but in a different region than the visceral region seen on PSMA PET.

13.3.3.3.  **$^{68}\text{Ga}$  PSMA-HBED-CC PET positive for osseous lesion by internal blind reader**, pathology (if available) is negative, and imaging after prostatectomy demonstrates that the osseous lesion is not positive for disease

13.3.3.3.1.  **$^{68}\text{Ga}$  PSMA-HBED-CC PET positive for osseous lesion by internal blind reader**, but pathology (if available) is positive for osseous lesion but in a different region than the osseous region seen on PSMA PET.

13.3.4. False negative region:

13.3.4.1.  **$^{68}\text{Ga}$  PSMA-HBED-CC PET negative for extra-pelvic nodes**

by internal blind reader, and pathology (if available) positive for that node, or, extra-pelvic node positive for disease by imaging as defined in Section 12.2.2.1.

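### True-positive rule 13.2.1.3 carries no PET-positive condition, and follow-up imaging can add true positives to the primary endpoint but never false negatives

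*Combined protocol and SAP*

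**What the plan says.** All references are to the combined protocol and SAP.

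- **True positive (13.2.1).** Items 13.2.1.1 and 13.2.1.2 both open with a PET/CT read positive for regional nodes by the internal blind reader. The second covers the pathology-negative man for whom "imaging after prostatectomy demonstrates the same node was not removed at surgery, and follow-up biopsy or imaging demonstrates presence of nodal disease". Item 13.2.1.3 is numbered in parallel but opens with "Conventional imaging criteria for positive node on follow-up imaging". It requires a decrease of more than 30% under treatment, "or increase by more than 20% in short axis diameter in the absence of treatment (with a minimum of 3 mm in change in size", and refers to 12.2.2.1. It names no PET result.
- **True negative (13.2.2.1).** PET negative, with "pathology at prostatectomy negative for regional nodes as defined in Section 12.2.1.2".
- **False negative (13.2.4.1, the only such rule).** PET negative, "but pathology at prostatectomy is positive for regional nodes". There is no imaging route.
- **Secondary endpoint, for contrast (13.3.4.1).** A PET-negative region is a false negative on positive pathology, "or, extra-pelvic node positive for disease by imaging as defined in Section 12.2.2.1".
- **Reference standard (12.2.2).** Follow-up imaging is secondary, for use when pathology is not available. One sentence states "All subjects will be tracked for follow-up conventional imaging between 3-12 months post" PET; a later one states "Follow up imaging will only be performed on subjects that have positive" PET findings. Section 6.4.2 collects standard-of-care imaging to 12 months without regard to the PET result.

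Section 13.2 gives no order of precedence among its cells.

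**The concern.** A true positive needs a positive index test. Item 13.2.1.3 does not ask for one, so its literal wording lets a node that PET missed count in PET's favour, and it lets one man occupy two cells of the 2x2 table.

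Behind the wording lies an asymmetry. Sensitivity is interpretable when disease is established by the same standard in PET-positive and PET-negative men. Here imaging can establish disease in the first group and not in the second.

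Section 13.1 says that the results will inform the target sensitivity for powering a larger study, possibly combined with other sites using the same reference definitions. It also names the reference standard as a particular source of uncertainty. An ambiguous or one-sided rule would carry forward into that design.

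**Working it through.** The plan's only numerical figures here are the half-widths in 13.1. They reproduce (for example 1.96 × √(0.80 × 0.20 / 30) = 14.3%) but do not bear on classification. The check is therefore a reading of the rules, followed by an illustration.

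**Step 1. Which cell does each type of man fall into?**

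| PET, pelvic nodes | Pathology | Later imaging | Cells met as worded |
|---|---|---|---|
| negative | negative | node meets size rule | true negative (13.2.2.1) and true positive (13.2.1.3) |
| negative | positive | residual node meets size rule | false negative (13.2.4.1) and true positive (13.2.1.3) |
| positive | negative | same node not removed, later shown diseased | true positive (13.2.1.2) |

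In no row does imaging create a false negative. Imaging also helps to decide false positives (13.2.3.1), but these do not enter sensitivity.

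**Step 2. Starting counts (assumption).** The documents do not say how many men would be affected. The prospective 30-man preoperative staging study in Section 2.3 reports sensitivity 64%, specificity 95%, PPV 88% and NPV 82%. The matching table is TP 7, FN 4, FP 1, TN 18: 7/11 = 63.6%, 18/19 = 94.7%, 7/8 = 87.5%, 18/22 = 81.8%.

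I use sensitivity = TP/(TP+FN). The formula printed in 13.1 has false positives in the denominator, which is PPV; that is a separate matter.

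**Step 3. Literal reading.** Add one PET-negative, pathology-negative man with a later imaging-positive node.

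| Scored as | Sensitivity | NPV |
|---|---|---|
| true positive | 8/12 = 66.7% | 18/22 = 81.8% |
| true negative | 7/11 = 63.6% | 19/23 = 82.6% |
| false negative (not available in 13.2) | 7/12 = 58.3% | 18/23 = 78.3% |

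The full spread in sensitivity is 66.7 − 58.3, or 8.3 points unrounded (1/12). Between the two cells that the wording allows, it is 8/12 − 7/11 = 3.0 points.

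If instead one of the 4 pathology-positive false negatives is moved to true positive (second row of Step 1), sensitivity goes from 7/11 = 63.6% to 8/11 = 72.7%.

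**Step 4. Intended reading.** Add one PET-positive, pathology-negative man who qualifies under 13.2.1.2. The plan gives 8/12 = 66.7%. With pathology as sole reference he is a false positive and sensitivity stays at 7/11 = 63.6%. The difference is 3.0 points, upward.

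**Step 5. Sensitivity to the starting counts.** The retrospective 130-patient study in Section 2.3 implies a node-positive share of (98.9 − 88.5)/(98.9 − 65.9) = 31.5%, about 9 of 30. Starting from TP 6, FN 3, the man in Step 3 gives 7/10 = 70.0%, 6/9 = 66.7% or 6/10 = 60.0%, a full spread of 10 points.

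**The case against.** The strongest reply is that 13.2.1.3 is a definition and not a patient state. Its lead-in speaks of criteria, it refers to the node as if already identified, and it supplies the size rule needed for the last step of 13.2.1.2. I think that is probably the intent. Nothing in 13.2 says so, however, and the item is numbered as a parallel route.

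Second, Section 12.2 appears to settle the overlap. Pathology is the primary determinant, imaging applies when pathology is not available, and objective 1.1.1 compares PET with pathology at prostatectomy. A PET-negative man with negative pathology would then be a true negative. This stands as the sensible reading, but 13.2 does not carry the precedence over. Under 12.2.1.5 imaging may still decide unsampled regions, and the exception in 12.2.1.2 concerns targeted tissue that was not resected, which does not clearly reach a man with no PET target.

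Third, follow-up imaging is limited to PET-positive subjects. This makes the affected group small but not empty. The limit is per subject, so a man positive only in bone can be imaged although his pelvic nodes were PET-negative, and standard-of-care imaging is collected for everyone.

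A reader might infer that the remedy is an imaging-based false-negative rule like that in 13.3.4.1. The documents do not support this for the primary endpoint. PET-negative men are imaged only as care happens to require, so the rule would verify them selectively and override negative pathology, against 12.2.2. Making absence of imaging disease a condition for a true negative would also conflict with 12.2.2.1, which bars imaging from establishing negativity.

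**Conclusion.** The wording of 13.2.1.3 is wrong for a true-positive rule and should be corrected. Read literally, it can score a PET-negative man as a true positive and place him in two cells. On the probable intended reading that fault disappears. The asymmetry does not: imaging can add true positives through 13.2.1.2 and can never add a false negative, so its only possible effect on sensitivity is upward.

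A reader might infer that the plan means to count PET misses as hits, or that the reported sensitivity will be inflated by 8 points. Neither is supported. Section 12.2.2 points the other way on intent, and the number of affected men is not given. The 8.3-point figure is the effect of one man, and it compares true positive with a false-negative cell that the plan does not offer him. The illustration assumes that a cited study's counts apply here. With about 9 to 11 node-positive men expected in 30, a single classification is still visible in the result.

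The trial is a descriptive pilot without significance testing, so this is a clarification that should be made and not a flaw that undermines the study.

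**What to change.** 1. Begin 13.2.1.3 with the condition that PET/CT is positive for a regional node by the internal blind reader and that the same node meets 12.2.2.1, or fold the item into 13.2.1.2. The two options differ for a PET-positive man who has no prostatectomy: the first could make him a true positive on imaging alone, while 13.2.3 would still need pathology to make him a false positive. The sponsor should choose knowingly.
2. State in 13.2 that PET-negative men with nodal pathology are classified by pathology alone, in line with objective 1.1.1 and Section 12.2.2, so that the cells are mutually exclusive.
3. Report sensitivity, specificity, PPV and NPV a second time with pathology at prostatectomy as the sole reference for all men. This applies one standard to PET-positive and PET-negative men and shows how much of the main result rests on imaging. It will count a PET-positive node left behind at surgery as a false positive, so it belongs beside the main table and does not replace it.

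The cost is wording and one extra tabulation, with no new imaging. Sensitivity may come out slightly less favourable.
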